Appendix 4. Sex-specific Framingham Risk Score algorithms

Framingham Risk Score (10-year CVD risk) for each subject is based on sex-specific Cox proportional hazard models.¹ Explicitly, the algorithm to compute Framingham Risk Score for each subject is:

$$\hat{p} = 1 - S_0(t)^{\exp(\sum_{i=1}^p \beta_i X_i - \sum_{i=1}^p \beta_i \bar{X}_i)},$$

where $S_0(t)$ is baseline survival at follow-up time t (10 years), β_i is the estimated regression coefficient (log hazard ratio), X_i is the log-transformed value of the i -th risk factor if continuous, \bar{X}_i is the corresponding mean, and p denotes the number of risk factors. For women, baseline 10-year survival is 0.95012. For men, the baseline 10-year survival is 0.88936.

Appendix 5. Manuscript Analyses

The following additional analyses will be performed for possible inclusion in a manuscript using the FAS. These results will not be included in the CSR. For analyses within a given baseline statin-intensity stratum, baseline statin-intensity stratum will not be included in the model (where appropriate).

- In addition to percent CFBL to Week 12 in LDL-C, all other secondary efficacy analyses will be conducted within each baseline statin-intensity stratum.

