9 OVERALL STATISTICAL CONSIDERATIONS

9.1 Sample Size Computation

The primary efficacy endpoint is the percent CFBL to Week 12 in LDL-C, with the primary focus on the overall set of randomized subjects. The efficacy within each baseline stable statin-intensity (high and moderate) stratum is also of interest for this study; thus, the study is powered for analysis within each baseline statin-intensity stratum. A sample size of 26 randomized subjects in the gemcabene 600 mg group and 26 randomized subjects in the placebo group within each baseline statin-intensity stratum is expected to provide 80% power to detect a difference of 17% in the percent CFBL to Week 12 in LDL-C between the gemcabene treatment group and the placebo group within each baseline statin-intensity stratum. This calculation is based on a 2-sided t-test at the 5% level of significance ($\alpha = 0.05$), a common standard deviation (SD) of 20, and a drop-out rate of 10%. The sample size of 26 randomized subjects in each baseline statin-intensity stratum in the gemcabene 600 mg group gives a total of 52 randomized subjects in the gemcabene 600 mg group. Twenty-six randomized subjects in each baseline statin-intensity stratum in the placebo group gives a total of 52 randomized subjects in the placebo group. Thus, the total study sample size is 104 randomized subjects.

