11.2 Secondary Analysis

All secondary analyses will be conducted using the FAS population (or the specific subgroup within the FAS population, eg, diabetic subjects) with subjects included in their randomized treatment group regardless of the treatment they actually received.

Similar analysis of ANCOVA as specified for the primary analysis in the above section will be conducted for the secondary efficacy endpoints. Note that the covariate included in the ANCOVA will be the baseline value of the parameter of interest (eg, if the parameter of interest is HDL-C, the covariate in the ANCOVA will be HDL-C at baseline).

As previous research suggests that hsCRP and TG are non-normally distributed,^{3,4,5} hsCRP and TG will be analyzed using ranked ANCOVA.⁶ Results of parametric ANCOVA will also be provided for these parameters as supportive results. Ranked ANCOVA will be conducted by first ranking the outcome and covariate at a given timepoint (eg, Week 12) prior to conducting ANCOVA. The p-value corresponding to the difference in ranked outcome between treatment groups will be output, and results will be interpreted in the context of the median change from baseline for each treatment group. The SAS code for conducting ranked ANCOVA is provided below (this can be extended to percent change from baseline):

```
proc rank data=data out=data_rank ties=mean;
    var base chg;
    ranks r_base r_chg;
run;

proc glm data=data_rank;
    class Drug(ref="Placebo") Diabetes StatinStrat;
    model r_chg = Drug Diabetes StatinStrat r_base / solution;
    lsmeans Drug / stderr pdiff cl out=adjmeans;
quit;
```

The secondary efficacy endpoints that are binary will be analyzed using logistic regression. The output from each logistic regression model will include the odds ratio (OR), 95% CI, and the associated p-value. The SAS code for conducting a logistic regression model is provided below:

```
proc logistic data=data;
    class Drug(ref="Placebo") Diabetes StatinStrat;
    model Outcome(event="event") = Drug Diabetes StatinStrat Base / expb;
run;
```

The secondary efficacy analyses are:

- percent CFBL to Week 12 in LDL-C within each statin-intensity stratum (moderate, high);
- CFBL to Weeks 2, 4, 8, and 12 in LDL-C;
- percent CFBL to Weeks 2, 4, and 8 in LDL-C;
- CFBL and percent CFBL to the average of Weeks 8 and 12 in LDL-C;
- CFBL and percent CFBL to Weeks 2, 4, 8, and 12 in non-HDL-C, TC, TG, HDL-C, and VLDL-C;

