- percent of subjects achieving a LDL-C reduction of $\geq 10\%$, $\geq 15\%$, and $\geq 20\%$ at Weeks 4, 8, and 12 (separately);
- percent of subjects achieving a LDL-C value < 100 mg/dL (2.59 mmol/L) at Weeks 4, 8, and 12 (separately);

- CFBL and percent CFBL to Weeks 4, 8 and 12 in ApoB, ApoA-I, ApoA-II, ApoA-V, ApoC-II, ApoC-III, ApoE, and Lp(a);
- CFBL and percent CFBL to Week 12 in hsCRP, SAA, adiponectin, and fibrinogen; and
- CFBL to Week 12 in Framingham Risk Score.

Percent CFBL to Week 12 in LDL-C within each statin-intensity stratum (moderate and high) will be analyzed using the same approach as the primary analysis except that baseline statin-intensity stratum will not be included in the model.

CFBL to Weeks 2, 4, 8, and 12 in LDL-C, percent CFBL to Weeks 2, 4, and 8 in LDL-C, and CFBL and percent CFBL to the average of Weeks 8 and 12 in LDL-C will be analyzed using the same approach as the primary analysis.

CFBL and percent CFBL to Weeks 2, 4, 8, and 12 in non-HDL-C, TC, TG, HDL-C, and VLDL-C, CFBL and percent CFBL to Weeks 4, 8 and 12 in ApoB, ApoA-I, ApoA-II, ApoA-V, ApoC-II, ApoC-III, ApoE, and Lp(a), and CFBL and percent CFBL to Week 12 in hsCRP, SAA, adiponectin, and fibrinogen will be analyzed using the same approach as the primary analysis, except that hsCRP and TG will be analyzed with ranked ANCOVA.

Percent of subjects achieving an LDL-C reduction of $\geq 10\%$, $\geq 15\%$, and $\geq 20\%$ at Weeks 4, 8, and 12 (compared to baseline), and percent of subjects achieving an LDL-C value < 100 mg/dL (2.59 mmol/L) at Weeks 4, 8, and 12 (compared to baseline) will be analyzed using logistic regression. Explicitly, we will estimate the odds of achieving the corresponding reduction (ie, $\geq 10\%$, $\geq 15\%$, and $\geq 20\%$) or an LDL-C value < 100 mg/dL at a given week using logistic regression. Randomized treatment group (gemcabene 600 mg or placebo), baseline statin-intensity stratum (moderate- or high-intensity), diabetes status (yes or no), and baseline LDL-C will be included in each model as factors.

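### The by-stratum responder odds ratios planned for the manuscript are fitted by ordinary maximum likelihood with about 26 subjects per arm, which overstates them modestly; Firth penalised likelihood is a cheap improvement.

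*SAP*

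**What the plan says.** SAP Appendix 5 states that, beyond the primary endpoint by stratum, "all other secondary efficacy analyses will be conducted within each baseline statin-intensity stratum", using the FAS and dropping the stratum term where that applies. Of this output it says: "These results will not be included in the CSR".

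SAP 11.2 lists the secondary analyses. Among them are the "percent of subjects achieving a LDL-C reduction of" at least 10%, 15% and 20%, and the percentage with LDL-C below 100 mg/dL, each at Weeks 4, 8 and 12. It says: "The secondary efficacy endpoints that are binary will be analyzed using logistic regression". The terms are treatment, statin-intensity stratum, diabetes and baseline LDL-C ("baseline LDL-C will be included in each model as factors"; the code leaves baseline LDL-C out of the CLASS statement, so it is fitted as a continuous covariate). The PROC LOGISTIC code carries only the expb option. It requests neither Firth nor exact estimation, so the fit is ordinary maximum likelihood. The promised output is an odds ratio, 95% CI and p-value. No rule covers separation or an empty cell, whereas the ANCOVA has assumption checks and a ranked fallback.

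SAP 9.1 sets 26 randomized subjects per arm per stratum, from a difference of 17 and "a common standard deviation (SD) of 20". SAP 9.2 treats secondary p-values as descriptive.

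**The concern.** Maximum-likelihood log odds ratios are biased away from zero in small samples. If one arm has no responders, or only responders, the treatment estimate does not exist. Both effects grow as the sample is split, so moving from 52 per arm overall to 26 per arm in a stratum makes them worse. At stake is the size of the stratum odds ratios that a manuscript might print. If a model failed after unblinding, there would also be no pre-stated rule for what to report. Efficacy by stratum is a secondary objective (SAP 5.2), so readers are likely to set the stratum and overall odds ratios side by side.

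**Working it through.** **Stratum size.** By the noncentral t (difference 17, SD 20, two-sided 0.05), 22 evaluable per arm gives power 0.786 and 23 gives 0.805. With 10% dropout, 23 / 0.90 = 25.6, so 26. The plan's figure is reproduced.

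**Number of models.** 3 reduction thresholds × 3 visits + 1 target × 3 visits = 12 per stratum, and 12 × 2 = 24.

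**Inputs.** From SAP 9.1: difference 17, SD 20, 26 per arm. Assumed, because the documents give no value: normal percent change, placebo mean 0 (also −5), 25% diabetic, and a distribution for baseline LDL-C.

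**Placebo response at mean 0**, Φ(−threshold / 20):
- at least 10%: Φ(−0.50) = 0.309, about 8 of 26
- at least 15%: Φ(−0.75) = 0.227, about 6 of 26
- at least 20%: Φ(−1.00) = 0.159, about 4 of 26

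**Bias.** Each simulated stratum (4,000 per scenario) was fitted with treatment, diabetes and baseline LDL-C. The target is the same model fitted to 200,000 subjects. Odds ratios are exp(mean log OR), with ML averaged over finite fits. Baseline LDL-C here is 100 plus a gamma variable, with the mean shown for the last two rows and 130 for the others.

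| Criterion | Target | ML | ML / target | Log bias | Firth |
|---|---|---|---|---|---|
| ≥10% | 3.99 | 4.48 | 1.12 | 1.500 − 1.385 = 0.115 | 3.94 |
| ≥15% | 4.00 | 4.75 | 1.19 | 1.557 − 1.385 = 0.172 | 4.12 |
| ≥20% | 4.19 | 4.85 | 1.16 | 1.578 − 1.433 = 0.145 | 4.20 |
| <100 mg/dL, mean 130 | 4.10 | 4.86 | 1.19 | 1.581 − 1.412 = 0.169 | 4.07 |
| <100 mg/dL, mean 145 | 4.32 | 5.13 | 1.19 | 1.634 − 1.463 = 0.171 | 4.18 |

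With a log-normal baseline (median 125, truncated at 100, log-SD 0.2) the ML and target values were 4.39 and 3.93, 4.64 and 3.99, 4.78 and 4.13, and 5.02 and 4.14: ratios 1.12, 1.16, 1.16 and 1.21. A further run gave ML 4.46 to 4.96 against targets 3.96 to 4.22. With a placebo mean of −5 (gamma baseline), the three reduction criteria gave 4.64 / 3.98 = 1.17, 4.55 / 3.97 = 1.15 and 4.63 / 3.95 = 1.17. A fair summary is 12% to 20%.

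**Bias against noise.** The SD of the ML log OR was 0.69 to 0.90, so the bias is roughly a fifth of one SD. Wald 95% coverage among finite fits was 95.4% to 96.8%. RMSE of the log OR was 0.68 to 0.90 for ML and 0.60 to 0.80 for Firth, lower for Firth on every criterion.

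**Infinite treatment odds ratio.** P(no placebo responder among 26) = (1 − p)^26:
- ≥10%: 0.691^26 = 0.0001
- ≥15%: 0.773^26 = 0.0013
- ≥20%: 0.841^26 = 0.011

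For <100 mg/dL the simulated rate was 0.3% (baseline mean 130) to 2.1% (mean 145), so about 1%. For all 24 models, an empty cell at 10% or 15% implies one at 20%. If the Week 12 inputs also hold at Weeks 4 and 8, the sum over 2 strata and 3 visits is at most 6 × (0.011 + 0.010) = 0.126. Simulation with visit correlation 0.6 gave 10% and 11% in two separate runs, below that bound as positive correlation requires.

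**Overall models for comparison.** At 52 per arm, ≥20%: ML 4.49 against 4.15 (ratio 1.08), Firth 4.14, and no separation.

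**The case against.** The strongest reply is that nothing breaks. Coverage is nominal, and a typical stratum interval is about exp(ln 4.5 ± 1.96 × 0.71), or 1.1 to 18. Beside that, a shift from 4.2 to 4.85 is hardly visible, and so is a stratum estimate of 4.85 beside an overall 4.49. Protocol 9.3.1.2 also asks for the responder percentage in each group next to each odds ratio, so a 0 of 26 cell would be seen for what it is. A profile-likelihood interval from ordinary ML would still give a finite lower bound. All of this stands, and it keeps the point minor. It does not remove the gain, because Firth is better on both bias and RMSE at almost no cost.

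Some stronger readings are tempting and are not supported:
- **That few placebo responders follows from the plan.** The plan gives a difference and an SD but no placebo mean. The 4 of 26 needs the assumed mean of 0 and describes only the 20% threshold; at 10% the figure is about 8.
- **That infinite odds ratios are likely.** Smaller SDs raise the chance sharply (about 45% for the 24 models at SD 15), but the documents give only SD 20.
- **That Firth cures everything.** It corrects the log odds ratio. For ≥20% the arithmetic mean of the odds ratio was 5.73 under Firth and 6.81 under ML, against a target of 4.19.

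**Conclusion.** The point holds as an optional refinement. At the plan's difference and SD, and under the stated assumptions on placebo mean, diabetes prevalence and baseline LDL-C, ordinary ML overstates the by-stratum responder odds ratios by about 12% to 20%. Confidence intervals remain sound. The chance of an infinite treatment estimate is about 1% in each of the more exposed models and roughly 10% across all 24. If the FAS is nearer 23 per arm the problem is slightly worse (≥20%: 5.01 / 4.15 = 1.21). The bias arises only if there is a treatment effect. A reader might infer that the planned inference is invalid or that the trial's conclusions are inflated; the documents do not support that, since these are descriptive analyses kept out of the CSR and the primary ANCOVA is untouched.

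**What to change.** In Appendix 5, state that the within-stratum responder models use Firth penalised likelihood with profile penalised-likelihood 95% CIs, by adding FIRTH and CLODDS=PL to the MODEL statement. In the simulations above this brought the odds ratio to within about 3% of target on the log-based measure, and every estimate was finite. It also settles in advance what to report if a cell is empty. Using the same option for the overall models in SAP 11.2 is optional and serves only comparability, since no separation arose there in the case checked.

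The cost is one sentence, a change to one MODEL statement and slightly smaller reported odds ratios. No extra data are needed.
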